10.9 Power for analysis of key secondary variables

Not Applicable

11 Ethical considerations and administrative procedures

11.1 Regulatory and ethical compliance

This clinical study was designed, shall be implemented and reported in accordance with the ICH Harmonized Tripartite Guidelines for Good Clinical Practice, with applicable local regulations (including European Directive 2001/20/EC and US Code of Federal Regulations Title 21), and with the ethical principles laid down in the Declaration of Helsinki.

11.2 Responsibilities of the investigator and IRB/IEC/REB

The protocol and the proposed informed consent form must be reviewed and approved by a properly constituted Institutional Review Board/Independent Ethics Committee/Research Ethics Board (IRB/IEC/REB) before study start. Prior to study start, the investigator is required to sign a protocol signature page confirming his/her agreement to conduct the study in accordance with these documents and all of the instructions and procedures found in this protocol and to give access to all relevant data and records to Novartis monitors, auditors, Novartis Clinical Quality Assurance representatives, designated agents of Novartis, IRBs/IECs/REBs and regulatory authorities as required.

11.3 Informed consent procedures

Eligible patients may only be included in the study after providing written (witnessed, where required by law or regulation), IRB/IEC/REB-approved informed consent.

Informed consent must be obtained before conducting any study-specific procedures (i.e. all of the procedures described in the protocol). The process of obtaining informed consent should be documented in the patient source documents. The date when a subject's Informed Consent was actually obtained will be captured in their CRFs.

Novartis will provide to investigators, in a separate document, a proposed informed consent form (ICF) that is considered appropriate for this study and complies with the ICH GCP guideline and regulatory requirements. Any changes to this ICF suggested by the investigator must be agreed to by Novartis before submission to the IRB/IEC/REB, and a copy of the approved version must be provided to the Novartis monitor after IRB/IEC/REB approval.

Women of child bearing potential should be informed that taking the study medication may involve unknown risks to the fetus if pregnancy were to occur during the study and agree that in order to participate in the study they must adhere to the contraception requirement for the duration of the study, and after treatment stop. If there is any question that the patient will not reliably comply, they should not be entered in the study.

Additional consent/information forms

Additional consent forms include:

- Information for female partners of male study participants
- Pregnancy follow-up for pregnant participants
- Pregnancy follow-up for the pregnant partner of participants

Male participants will be requested to provide the Information for female partners of male study participants form to their partners.

11.4 Discontinuation of the study

Novartis reserves the right to discontinue this study under the conditions specified in the clinical study agreement. Specific conditions for terminating the study are outlined in [Section 7.1.5](#).

11.5 Publication of study protocol and results

Novartis is committed to following high ethical standards for reporting study results for its innovative medicine, including the timely communication and publication of clinical trial results, whatever their outcome. Novartis assures that the key design elements of this protocol will be posted on the publicly accessible database, e.g. www.clinicaltrials.gov before study start. In addition, results of interventional clinical trials in adult patients are posted on www.novartisclinicaltrials.com, a publicly accessible database of clinical study results within 1 year of study completion (i.e., LPLV), those for interventional clinical trials involving pediatric patients within 6 months of study completion.

Novartis follows the ICMJE authorship guidelines (www.icmje.org) and other specific guidelines of the journal or congress to which the publication will be submitted.

Authors will not receive remuneration for their writing of a publication, either directly from Novartis or through the professional medical writing agency. Author(s) may be requested to present poster or oral presentation at scientific congress; however, there will be no honorarium provided for such presentations.

As part of its commitment to full transparency in publications, Novartis supports the full disclosure of all funding sources for the study and publications, as well as any actual and potential conflicts of interest of financial and non-financial nature by all authors, including medical writing/editorial support, if applicable.

For the Novartis Guidelines for the Publication of Results from Novartis-sponsored Research, please refer to www.novartis.com.

11.6 Study documentation, record keeping and retention of documents

Each participating site will maintain appropriate medical and research records for this trial, in compliance with Section 4.9 of the ICH E6 GCP, and regulatory and institutional requirements for the protection of confidentiality of subjects. As part of participating in a Novartis-sponsored study, each site will permit authorized representatives of the sponsor(s) and regulatory agencies to examine (and when required by applicable law, to copy) clinical records for the purposes of quality assurance reviews, audits and evaluation of the study safety and progress.

Source data are all information, original records of clinical findings, observations, or other activities in a clinical trial necessary for the reconstruction and evaluation of the trial. Examples of these original documents and data records include, but are not limited to, hospital records, clinical and office charts, laboratory notes, memoranda, subjects' diaries or evaluation checklists, pharmacy dispensing records, recorded data from automated instruments, copies or

transcriptions certified after verification as being accurate and complete, microfiches, photographic negatives, microfilm or magnetic media, x-rays, and subject files and records kept at the pharmacy, at the laboratories, and medico-technical departments involved in the clinical trial.

Data collection is the responsibility of the clinical trial staff at the site under the supervision of the site Principal Investigator. The study case report form (CRF) is the primary data collection instrument for the study. The investigator should ensure the accuracy, completeness, legibility, and timeliness of the data reported in the CRFs and all other required reports. Data reported on the CRF, that are derived from source documents, should be consistent with the source documents or the discrepancies should be explained. All data requested on the CRF must be recorded. Any missing data must be explained. Any change or correction to a paper CRF should be dated, initialed, and explained (if necessary) and should not obscure the original entry. For electronic CRFs an audit trail will be maintained by the system. The investigator should retain records of the changes and corrections to paper CRFs.

The investigator/institution should maintain the trial documents as specified in Essential Documents for the Conduct of a Clinical Trial (ICH E6 Section 8) and as required by applicable regulations and/or guidelines. The investigator/institution should take measures to prevent accidental or premature destruction of these documents.

Essential documents (written and electronic) should be retained for a period of not less than fifteen (15) years from the completion of the Clinical Trial unless Sponsor provides written permission to dispose of them or, requires their retention for an additional period of time because of applicable laws, regulations and/or guidelines.

11.7 Confidentiality of study documents and patient records

The investigator must ensure anonymity of the patients; patients must not be identified by names in any documents submitted to Novartis. Signed informed consent forms and patient enrollment log must be kept strictly confidential to enable patient identification at the site.

11.8 Audits and inspections

Source data/documents must be available to inspections by Novartis or designee or Health Authorities.

11.9 Financial disclosures

Financial disclosures should be provided by study personnel who are directly involved in the treatment or evaluation of patients at the site - prior to study start.

12 Protocol adherence

Investigators ascertain they will apply due diligence to avoid protocol deviations. Under no circumstances should the investigator contact Novartis or its agents, if any, monitoring the study to request approval of a protocol deviation, as no authorized deviations are permitted. If the investigator feels a protocol deviation would improve the conduct of the study this must be considered a protocol amendment, and unless such an amendment is agreed upon by Novartis

and approved by the IRB/IEC/REB it cannot be implemented. All significant protocol deviations will be recorded and reported in the CSR.

## Document History – Changes compared to previous final version of SAP

Date	Time point	Reason for update	Outcome for update	Section and title impacted (Current)
22-Aug-2017	Prior to FPFV	N/A – Initial version	N/A	N/A
14-Jan-2020	Prior to database lock	Rules to select one assessment among several assessments in the same visit	Selection of assessment to analyze among multiple values in the same visit	2.1.5
		Time windows for unplanned visits	Time windows to assign unplanned visits in scheduled ones	
		Added rules to assign patients to 7+3 and 5+2 groups	Patients who do not have exactly 7+3 or 5+2 are assigned	2.1.8
		Category/Value missing	Added treatment exposure category “>28”. Cardiac imaging changed “>” to “>_” for 20	2.4.2 2.8.4.2
		Change in CSR template	Concomitant medications will be analyzed with FAS instead of SAF	2.4.3
		Clinical efficacy response derivation and subgroup analyses	Selection of best response among several assessment in the same period. Response analyzed by sex	2.6.1
		AEs by subgroup	AEs to be analyzed by age category	2.8.1
		Resource utilization updated to CRF	Updated with variables only included in CRF	2.13.3
		Additional details on imputation rules	Derivation rules updated	6.1
		BUN/Urea imputation rules	To impute BUN or Urea missing values	6.2
26-Jun-2020	Study treatment exposure	Rules od study treatment exposure clarified.		2.1.1
		Analysis set	All enrolled subjects added	2.2
	Subgroups analyses added : type of induction drugs		Efficacy and safety outputs provided by Idarubicin and Daunorubicin.	2.3
	Age subgroups		<= 60 vs. >60 instead of <60 vs. >=60	2.3 and 2.4.2

Date	Time point	Reason for update	Outcome for update	Section and title impacted (Current)
		Efficacy	If patient discontinued prior to first efficacy assessment then 'unknown' is assigned as best response	2.7.1
15-Jun-2021	Prior to database lock	PD	The number (%) of protocol deviations with COVID-19 relationship will be presented by type of deviation for all enrolled subjects.	2.5.4
09-Nov-2021	Post to database lock	Subgroups analysis amended for a new agesubgroup/category.	Included the following age subgroup/category: <= 60 / >60 to <=70 / > 70 years old	2.3, 2.4.2, 2.5.2 and 2.7.1
<hr/> 
FPFV: First patient first visit
 <hr/>				

## List of abbreviations

AE	adverse event
AESI	adverse events of special interest
ALT	aspartate aminotransferase
AML	acute myeloid leukemia
Ara-C	cytarabine, also known as cytosine arabinoside
AST	alanine aminotransferase
ATC	anatomical therapeutic chemical classification
CIVI	continuous intravenous infusion
CR	complete remission
CRi	complete remission with incomplete recovery
CRS	case retrieval sheet
CSR	clinical study report
CTCAE	common terminology criteria for adverse events
DI	dose intensity
ECG	electrocardiogram
ECOG	eastern cooperative oncology group
eCRF	electronic case report form
<hr/>	
FAS	full analysis set
FLT3	fms-like tyrosine kinase receptor
GPS	global programming & statistical environment
IV	intravenous
LPLV	last patient last visit
LVEF	left ventricular ejection fraction
MedDRA	medical dictionary for drug regulatory affairs
MUGA	multi gated acquisition scan
NCCN	national comprehensive cancer network
NCDS	Novartis clinical data standards
PD	pharmacodynamics
PDS	programming data specifications
<hr/>	
PK	pharmacokinetics
<hr/>	
PT	preferred term
QTc	corrected QT interval
SAE	serious adverse event
SAP	statistical analysis plan
SI	international system of units
SOC	system organ class
TFLs	tables, figures, listings
WHO	world health organization

## 1 Introduction

This statistical analysis plan (SAP) provides detailed statistical methodology for the analyses of data which will be used for preparation of the PKC412A2408 clinical study report (CSR) and is based on the study protocol Amendment 1, dated 26-Mar-2018. At the time of this amendment, enrollement was completed with 301 patients.

The shells for the in-text tables and figures as well as the post-text tables, figures and listings (TFLs) are in the TFL shells document. Programming specifications for datasets, including derivation of variables, are given in the programming data specifications (PDS) document.

All data will be analyzed by Novartis using Novartis clinical data standards (NCDS). Analysis data sets and statistical outputs will be produced using the SAS system Version 9.4 or higher (UNIX environment) in the global programming & statistical (GPS) environment.

### 1.1 Study design

This is an open-label, single arm, multicenter, Phase IIIb study of midostaurin (PKC412 or CGP41251) in adults with newly-diagnosed fms-like tyrosine kinase receptor (FLT3)-mutated acute myeloid leukemia (AML) who have started on “7+3” or “5+2” induction chemotherapy.

The purpose of this study is to gather and evaluate additional safety and efficacy data on the combination of midostaurin and standard of care.

[figure not shown]
Midostaurin is used in combination with chemotherapy sequentially in **induction** and **consolidation** phase and as a single agent in **maintenance** phase as outlined in [Figure 1-1](#).

Approximately 300 patients are planned to be enrolled.

No formal interim analyses are planned.

The final (primary) analysis will be performed after database lock when all patients have either completed the study as per protocol (including their safety evaluation 30 days after the last dose of study treatment) or they have prematurely discontinued.

[figure not shown]
**Figure 1-1** Study design

Complete remission (CR): Bone marrow blasts <5%; absence of blasts with Auer rods; absence of extramedullary disease; absolute neutrophil count (ANC) >1.0 x10^9/L; platelet count >100 x 10^9/L; independence of red cell transfusions

CR with incomplete recovery (CRi): All CR criteria except for residual neutropenia (<1.0 x10^9/L) or thrombocytopenia (<100 x 10^9/L)

**Figure 1-2** Recovery periods

## 1.2 Study objectives and endpoints

Objective	Endpoint
Primary	
To further assess the safety of midostaurin in induction, consolidation and maintenance therapy, including, the "7+3" regimen, daunorubicin (60-90mg/m  /day), the substitution of daunorubicin by idarubicin (12mg/m  /day), cytarabine (100-200 mg/m  /day) and also allowing the "5+2" reduced dose regimen.	Proportion of patients with AEs, Grade 3&4 AEs, SAEs, AEs leading to discontinuation, and deaths.
Secondary	
To assess the clinical efficacy of midostaurin in combination with chemotherapy regimens in induction and consolidation and the clinical efficacy of midostaurin maintenance phase (measured by CR/CRI rate).	Proportion of patients with CR/CRI as per local assessment
Exploratory	
To assess resource utilization	Proportion of patients by reason for hospitalization, number of hospital days, discharge reason and concomitant medications taken during hospital stay
AE: adverse event	

## 2 Statistical methods

### 2.1 Data analysis general information

Categorical data will be presented as frequencies and percentages. For continuous data, n, mean, standard deviation, median, 25th and 75th percentiles, minimum, and maximum will be presented.

The data from all centers that participate will be combined in the analyses.

Final (primary) analysis will be performed after database lock has occurred (after last patient last visit (LPLV)).

#### 2.1.1 General definitions

The overall observation period is divided into the following **mutually exclusive** periods:

1. **Pre-treatment:** from day of patient's informed consent to the day before first dose of midostaurin

2. **On-treatment:** from start date of midostaurin to last date of study treatment + 30 days.

Further details provided in [Section 2.1.3](#).

On-treatment includes 3 mutually exclusive periods:

- a. **Induction** period: From day of first dose of midostaurin to the day before start of consolidation period (i.e. end of induction phase plus any rest/recovery days).  
Up to 2 cycles (28 days of treatment/cycle and a recovery period)
- b. **Consolidation** period: From day of first dose of study treatment in consolidation phase to the day before start of maintenance (i.e. end of consolidation phase plus any rest/recovery days).  
Up to 4 cycles (28 days of treatment/cycle and a recovery period)
- c. **Maintenance** period: From day of first dose of midostaurin in the maintenance phase to the date of last dose of midostaurin + 30 days.  
Up to 12 cycles (28 days of treatment/cycle)

It is noted that if a patient permanently discontinues study treatment during any of these periods, on-treatment is considered until the date of last dose of study treatment + 30 days (unless patient withdraws study informed consent or dies before then, then it is till the withdrawal/death date)

3. **Post-treatment:** from last date of study treatment + 31 days to end of study

Each period will contain all patients who entered that period (incl. withdrawal, drop-outs etc.)

### **Study drug and study treatment**

Study drug refers to the individual drugs used in the study after signing of informed consent, i.e. the Novartis investigational drug midostaurin, or its partners, cytarabine and daunorubicin (or idarubicin).

Study treatment refers to any component of the study drugs, midostaurin, cytarabine and daunorubicin (or idarubicin).

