4.1 Description of study

This is an open-label, multi-centre, phase IIIb study in patients 18 years of age or older with newly-diagnosed FLT3-mutated Acute Myeloid Leukemia (AML) who have started “7+3” or “5+2” chemotherapy regimen.

Investigators must obtain FLT3 testing results prior to ICF signature in order to allow patients to initiate midostaurin treatment per protocol.

NPM1 mutation status will also be collected if available.

[figure not shown]
The protocol treatment will allow the following treatment phases:

- Induction phase: 1 or 2 cycles of “7+3” or “5+2” regimens (switching between regimens is not allowed).
- Consolidation phase: up to 4 cycles of cytarabine consolidation, with midostaurin given sequentially during each cycle,
- Maintenance phase: up to 12 cycles of maintenance therapy with single-agent midostaurin or until relapse, unacceptable toxicity, or death, physician’s decision, subject/guardian’s decision, protocol deviation, study termination by sponsor, lost to follow-up, technical

problems, pregnancy, subject withdrew consent or until the end of study, whichever event occurs first.

The estimated study duration is about 3.5 years, including about 18 months for recruitment and around 18 to 25 months for completion of the induction, consolidation and maintenance therapy.

[figure not shown]
Figure 4-1 Study design

Chemotherapy - First induction cycle					
Day -2	Day -1	Day 1 to Day 6	Day 7	Day 8	Day 9 to Day 28
Study start					
AML Diagnosis	AML Diagnosis	"7+3" or "5+2" chemotherapy	Screening / Baseline Day -1	Enrollment Day 1	Study treatment
FLT3 testing up to Day 6					

Figure 4-2 Recovery periods

R = Recovery

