7.1.2 Screening

Patients who are newly diagnosed with AML, have a known FLT3 ITD or TKD mutation and who have already started a “7+3” or “5+2” chemotherapy regimen in first induction will be consented and screened during the screening/baseline period (between C1D1 (chemotherapy already started) to C1D7) at least all the activities should be completed at Day 7 of the first chemotherapy (at Day -1). Re-screening is not allowed in this study.

The historical BMA result used to diagnose AML to the patients can be considered a part of inclusion criteria in the study.

If an historical BMA is available within 15 days before C1D1 of the first chemotherapy there is no need to repeat this assessment during the screening/baseline period.

If in case an historical BMA is not available within the 15 days before C1D1 of the first chemotherapy, a BMA should be performed during the screening/baseline period of the study.

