7.1.2.3 Patient demographics and other baseline characteristics

Baseline patient data pertaining to demographic information and relevant medical history related to study indication should be documented accordingly in the eCRFs including, but not limited to, the following information:

- Demography (including: date of birth, age, patient initials, gender, childbearing potential, race and ethnicity, or as allowed by local regulations)
- Relevant medical history
- Date of diagnosis
- Physical Examination (Height, Weight, Vital Signs)
- Performance status
- FLT3 mutation status (ITD or TKD)
- Bone marrow aspiration
- Any additional mutation information, if known
- Prior and Concomitant Medications
- Surgical and Medical Procedures
- Chemotherapy information from induction cycle 1 day 1 to day 7

Additionally all other medications and significant non-drug therapies taken within 28 days prior to the first dose of midostaurin being administered must be recorded on the eCRF page and updated on a continual basis if there are any new changes to the medication. Medications include Investigator prescriptions and over-the-counter medications, vitamins, and herbal and alternative therapies.

Information to be collected on concomitant medications/significant non-drug therapies will include the following:

- Medication/Non-drug therapy trade name
- Reason for medication
- Start/End date and if continuing at time of examination

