### **Date of first administration of study treatment**

The date of first administration of study treatment (will be midostaurin for all patients) is derived as the first date when a nonzero dose of any component of study treatment is administered. It is derived by period (induction, consolidation, maintenance) and overall.

For example, if the 1st dose of midostaurin is taken on 08-Feb-2016, and 1st dose of a combination partner (e.g. cytarabine), is taken on 01-Feb-2016, then the date of first administration of study treatment is 01-Feb-2016. The date of first administration of study treatment is also referred to as ***start date of study treatment***.

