### **Actual cumulative dose**

Cumulative doses will be derived for each of the study drugs: midostaurin, daunorubicin and idarubicin.

The actual cumulative dose refers to the total actual dose administered, over the duration for which the patient is on study drug as documented in the dose administration eCRF.

For patients who did not take any study drug, the actual cumulative dose is by definition equal to zero.

The actual cumulative dose is the sum of the non-zero doses recorded over the study drug dosing periods. Rest periods are not included.

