### **2.1.8 Chemotherapy group assignment**

Patients will be assigned to '7+3' or '5+2' chemotherapy groups considering the following rules of the first induction cycle:

- If cytarabine duration is  $\geq$  7 days, '7+3' group will be assigned, without considering the duration of daunorubicin/idarubicin.
- If cytarabine duration is  $<$  7 days, '5+2' group will be assigned, without considering the duration of daunorubicin/idarubicin.

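### SAP 2.1.1 limits study drug to drugs used after consent, although induction chemotherapy normally starts before consent; applied literally, this would distort the 7+3/5+2 grouping and first-cycle anthracycline exposure

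*SAP*

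**What the plan says.** **The definition.** SAP 2.1.1, Study drug and study treatment: "Study drug refers to the individual drugs used in the study after signing of informed consent". The sentence goes on to list midostaurin and its partners cytarabine and daunorubicin or idarubicin.

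**What uses it.** In SAP 2.1.1, the first and last dates, the per-cycle duration of cytarabine and the anthracyclines, and the cumulative dose and dose intensity of the anthracyclines are all expressed in terms of study drug. On cumulative dose it adds: "For patients who did not take any study drug, the actual cumulative dose is by definition equal to zero". SAP 2.1.8 puts a patient in 7+3 if first-cycle cytarabine lasted at least 7 days. For anything shorter, the "5+2' group will be assigned, without considering the duration of daunorubicin/idarubicin".

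**When consent is given.** Inclusion criterion 5 requires that first induction has already started. Protocol 7.1.2 places consent and screening "between C1D1 (chemotherapy already started) to C1D7". Protocol 4.1 adds: "Investigators must obtain FLT3 testing results prior to ICF signature", and its design schema shows FLT3 testing up to Day 6.

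**What points the other way.** In the SAP's example for the start of study treatment, cytarabine begins on 01-Feb-2016 and midostaurin on 08-Feb-2016; "then the date of first administration of study treatment is 01-Feb-2016". Protocol 7.1.2.3 lists among the baseline data: "Chemotherapy information from induction cycle 1 day 1 to day 7".

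**The concern.** The after-consent clause suits midostaurin, which starts on Day 8. It does not suit the first-cycle chemotherapy, part or all of which can precede the signature by design. The only cytarabine duration that the SAP defines is the one built on study-drug dates, so a programmer could reasonably feed that duration into the 2.1.8 rule. Regimen group and anthracycline exposure would then depend on the day the form was signed as well as on the treatment given.

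This matters because the primary objective is safety across 7+3, 5+2 and the choice and dose of anthracycline, and SAP 2.3 reports safety and efficacy by chemotherapy group and by type of induction drug. Full-intensity patients placed in the 5+2 column would blur the contrast that these displays are meant to describe.

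**Working it through.** **Inputs.**
- Consent on cycle day k, k = 1 to 7 (Protocol 7.1.2).
- 7+3: cytarabine on Days 1-7 as a 168-hour infusion; daunorubicin 60-90 or idarubicin 12 mg/m²/day on Days 1-3 (Protocol Table 6-1, SAP Table 2-1).
- Duration in a cycle = last date − first date + 1 (SAP 2.1.1).
- Cut at 7 cytarabine days (SAP 2.1.8).

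**The plan's own figure.** With midostaurin on Day 8 dated 08-Feb-2016, Day 1 is 08-Feb minus 7 days = 01-Feb-2016. This is the date the SAP gives, so the example counts chemotherapy from Cycle 1 Day 1. It agrees with the after-consent clause only if consent was signed by 01-Feb, and no consent date is given. The same paragraph says in parentheses that the first study treatment is midostaurin for everyone, which its own example contradicts.

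**Literal after-consent reading.** Let f be the first counted day: f = k if consent-day doses count, k + 1 if not. Let e be the last cytarabine date: 7, or 8 if the 168-hour infusion is dated into Day 8. Then:
- cytarabine days = e − f + 1
- anthracycline doses = max(0, 3 − f + 1)

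For a full 7+3 course with f = k and e = 7:

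| Consent day | Cytarabine days | Group | Anthracycline doses | Daunorubicin, mg/m² | Idarubicin, mg/m² |
|---|---|---|---|---|---|
| 1 | 7 | 7+3 | 3 | 180-270 | 36 |
| 2 | 6 | 5+2 | 2 | 120-180 | 24 |
| 3 | 5 | 5+2 | 1 | 60-90 | 12 |
| 4 | 4 | 5+2 | 0 | 0 | 0 |
| 5 | 3 | 5+2 | 0 | 0 | 0 |
| 6 | 2 | 5+2 | 0 | 0 | 0 |
| 7 | 1 | 5+2 | 0 | 0 | 0 |

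**Sensitivity to the dating convention.**

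| Consent-day doses | Last cytarabine date | Grouped 5+2 from consent on | First-cycle anthracycline zero from consent on |
|---|---|---|---|
| counted | Day 7 | Day 2 | Day 4 |
| not counted | Day 7 | Day 1 | Day 3 |
| counted | Day 8 | Day 3 | Day 4 |
| not counted | Day 8 | Day 2 | Day 3 |

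Under all four conventions, consent on Day 3 or later gives 5+2 and consent on Day 4 or later gives no first-cycle anthracycline.

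**Dose intensity behaves differently.** With m equal daily doses d left in the first cycle, cumulative dose is m × d and duration is m, so intensity is d. It is unchanged while any dose remains. If none remains and no later anthracycline is given, the SAP's rule for patients with no study drug sets it to zero.

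**A true 5+2 course.** Five days of cytarabine (six if dated on by a day) is below 7 whatever the consent day, so the group is unchanged. Any regrouping therefore runs one way, from 7+3 to 5+2.

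**Counting from Cycle 1 Day 1.** A full 7+3 course gives 7 cytarabine days (8 if dated into Day 8), group 7+3, three anthracycline doses, and 3 × 60-90 = 180-270 mg/m² daunorubicin or 3 × 12 = 36 mg/m² idarubicin, for every consent day.

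**The case against.** A reader might infer that 7+3 patients are in fact reported as 5+2 with their anthracycline dose cut. The documents do not support that, for these reasons:

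- The definition can be read as naming the drugs rather than filtering doses, and no text says that pre-consent doses are discarded.
- SAP 2.1.8 speaks of cytarabine duration in the first induction cycle and sets no consent limit.
- The document history says that rule was added for patients whose regimen was not exactly 7+3 or 5+2, which presupposes that the regimen given is known.
- The subgroups by daunorubicin dose and idarubicin in SAP 2.3 likewise presuppose the doses given.
- The zero-dose sentence describes patients who took no drug; it does not itself turn pre-consent doses into zeros.
- Derivations sit in a programming specification that is not among the documents.

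All of this stands, and it makes the point a conflict to resolve rather than a demonstrated error. It does not remove the conflict. The 01-Feb example concerns study treatment, not study drug, and contradicts its own parenthesis. The Day 1-7 chemotherapy is listed as baseline data, whereas cumulative dose is drawn from the dose administration eCRF. Nothing states that pre-consent doses count, so two programmers could follow this SAP and form different groups.

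Nor would every 7+3 patient be affected on the literal reading. Consent on Day 1 with that day's doses counted keeps the patient in 7+3, and Protocol 2.2 also lets chemotherapy begin while screening is under way. It is also tempting to say that sites with slower FLT3 results would appear to give less chemotherapy; without consent-day data that is conjecture.

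**Conclusion.** The conflict is real and should be removed. Applied literally, the consent limit would group full 7+3 courses as 5+2 for consent after about Day 1 or 2. It would understate first-cycle anthracycline, to zero for consent from about Day 3 or 4. Doses in a second induction would still count in the period and overall totals. These figures assume a complete 7+3 course given on the scheduled days, and the range reflects the four dating conventions.

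The number of patients affected cannot be computed, because no consent-day distribution is given. The overall safety result is not in question: the safety set needs one dose of midostaurin, the adverse event window opens at first midostaurin, and no hypothesis is tested. What is at risk is the results by regimen and by type of induction drug, and the descriptive chemotherapy exposure.

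**What to change.** 1. In SAP 2.1.1, remove the consent limit for first-cycle chemotherapy.
2. State that all first-induction cytarabine and anthracycline doses from Cycle 1 Day 1, including those before consent, count for duration, cumulative dose, dose intensity and the group assignment in 2.1.8.
3. Name the eCRF page or pages from which these doses are taken.
4. Reconcile the parenthesis on the first study treatment with its 01-Feb-2016 example.
5. Keep the adverse event window starting at first midostaurin. Because the induction period in SAP 2.1.1 also starts there, say that the induction exposure summaries nevertheless include Days 1-7 of the first cycle.
6. Check that the programmed regimen groups and anthracycline totals follow this rule, and correct the affected outputs if they do not.

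The cost is wording in the SAP and programming specification plus one check of the derived variables. Protocol 7.1.2.3 already provides for collecting the chemotherapy data.
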